## **1. STUDY DESIGN**

In this pilot study we will use an ultrasound probe that is currently clinically used to assess pituitary anatomy, the Hitachi-Aloka high resolution pituitary transducer to measure left ventricular (LV) septal thickness during cardiopulmonary bypass in the performance of surgical septal myectomy. We will assess if septal thickness can be visualized during the procedure and if it is likely to improve the efficacy and safety of the procedure. The probe has FDA clearance for a variety of intra-operative surgical procedures but will be off-label for this cardiac surgical protocol. Attached is a memo from the manufacturer stating the device does not meet criteria of a “significant risk device” as per 21 CFR 812.3(m).

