## **3. RATIONALE**

There is currently no way to monitor the depth of surgical septal myectomy during the on-pump period in the OR. This is because the heart is empty of blood and transesophageal echocardiography (TEE) imaging is impossible. Also epicardial imaging is impossible. The brochure (attached separately) shows the probe we believe will let us image the septum. It may make the surgical procedure more accurate and decrease complications of “too little myectomy” or “too much myectomy”. Both can decrease the need for reoperation which is currently a risk of myectomy 1-2%. The probe is a sterile one-time-use device. The transducer itself is 2.9 mm in diameter. We have tested the probe in a simulation similar to that we will encounter during Hypertrophic Cardiomyopathy (HCM) surgery and there was excellent visualization of muscular thickness with 1:1 correlation with conventionally measured muscular wall and the ultrasound visualized thickness.

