## **4. METHODS AND PROCEDURES**

Subjects will be volunteer patients with hypertrophic cardiomyopathy who will be undergoing myectomy from the HCM Program. Before cardiopulmonary bypass the anterior septal thickness at the point of mitral-septal contact will be measured by TEE in 120 degree view. The distance from the aortic annulus of this location will also be noted. With OPIE the PI will measure this thickness at the

site of mitral-septal contact as assessed by the location of the contact lesion (callous) and confirmed by the cm below the aortic annulus. After resection the residual thickness of the septum will be measured both by OPIE and by post-cardiopulmonary bypass TEE. The thickness of the surgical specimen will be measured. The differences between the OPIE and TEE measured septal thicknesses provide the primary data points for the statistical analysis.

We estimate that the cardiopulmonary bypass time of the OPIE will be prolonged 3 minutes. This may be offset by faster myectomy time gained by more confidence of septal thickening. Length of stay should not be prolonged.

We will enroll 10 subjects in this pilot study. Subject participation will be complete after their hospitalization for surgery. No follow-up visits are necessary, outside of the routine post-op care.

In general, results from studies, which use data, collected as part of this research will be preliminary, and the clinical implications of any findings may not be understood for years. Therefore, individual study results will not be disclosed to the patient and/or his or her healthcare provider(s). Data will be stored in a database housed within the Department of Cardiothoracic Surgery. The above mentioned database will be stored until the end of the study in a password protected secure computer server accessible only by the principle investigator, co-investigators and research staff listed for this project.

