#### **Sample size and data analysis:**

Each of the 10 patients will have 4 measurements(OPIE & TEE before cardiopulmonary bypass and OPIE & TEE after cardiopulmonary bypass) in the septum using two techniques (TEE and OPIE Ultrasound Probe). Primary outcome is the the difference between TEE measured septal thickness and the OPIE measured thickness before and after cardiopulmonary bypass. Center tendency parameters(mean, standard deviation) will be reported for each outcome. For example: we will report the mean and standard deviation for the difference between TEE measured septal thickness and OPIE measured thickness before and after cardiopulmonary bypass. The OPIE and TEE measurements will be compared both before and after cardiopulmonary bypass for each of the outcome as well. Accurate myectomy residual thickness is vital for success of this operation. The clinical utility of the OPIE probe will be shown if there is a  $\geq 2$ mm difference (either greater than or less than) between any single OPIE measurement and the TEE measurement either before cardiopulmonary bypass or after cardiopulmonary bypass. Given the critical nature of the assessment of septal thickness, even a 2-4 mm difference in just one patient (10% of patients) is deemed essential information.

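### Clinical utility is declared if any one of 20 OPIE–TEE differences reaches 2 mm, a rule that an inaccurate probe meets more easily than an accurate one

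*Combined protocol and SAP*

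**What the plan says.** Section 4 sets the size of the study: "We will enroll 10 subjects in this pilot study". Under its sample size and data analysis heading, each patient has one OPIE and one TEE reading at each of two time points, and the primary outcome is the difference between the methods. For that outcome, "we will report the mean and standard deviation for the difference between TEE measured septal thickness and OPIE measured thickness" at both time points, and the two methods will be compared.

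The conclusion comes from a separate rule. "The clinical utility of the OPIE probe will be shown if there is a" difference of 2 mm or more, in either direction, "between any single OPIE measurement and the TEE measurement either before cardiopulmonary bypass or after cardiopulmonary bypass". The justification is that "even a 2-4 mm difference in just one patient (10% of patients) is deemed essential information".

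No other criterion for utility or success appears. Section 1 says "We will assess if septal thickness can be visualized during the procedure" and that likely effects on efficacy and safety will be considered, but attaches no criterion to either.

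Two further statements bear on what a difference means. Section 3 explains why depth cannot now be monitored on pump: "This is because the heart is empty of blood and transesophageal echocardiography (TEE) imaging is impossible". Section 4 says: "After resection the residual thickness of the septum will be measured both by OPIE and by post-cardiopulmonary bypass TEE".

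**The concern.** A difference between two methods is evidence of disagreement, not of which one is right. The rule counts disagreement in either direction as proof of the probe's value, so every source of OPIE error raises the chance of a favourable conclusion. A probe that tracked TEE closely would have no route to one. The rule is a sufficient condition, so such a probe is not declared a failure, but it could never meet the only criterion stated.

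The two readings in a pair also appear to be taken in different states of the heart. Sections 1 and 2 place OPIE during bypass. Section 3 says TEE cannot image then, and Section 4 takes TEE before and after bypass. A 2 mm difference could therefore arise with neither device in error and still be scored as utility.

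At stake is the headline of the pilot. Followed as written, one discrepant reading supports the statement that clinical utility has been shown, even if the probe made the error.

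**Working it through.** **Inputs from the plan.** 10 patients; 2 OPIE–TEE pairs per patient; threshold 2 mm in either direction; one qualifying pair is enough. The plan's own figure reproduces: 1/10 = 10% of patients. The number of chances is 10 × 2 = 20 pairs.

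**Inputs the plan does not give.** The SD and the mean (bias) of the OPIE–TEE difference. Both are assumed below and shown as a range.

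**Formula.** Let b be the mean OPIE–TEE difference and take the differences as normal. For one pair,

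p = 1 − [Φ((2 − b)/SD) − Φ((−2 − b)/SD)].

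The chance that the rule is met is 1 − (1 − p)^k. Here k = 10 if the two pairs within a patient are fully dependent and k = 20 if all pairs are independent.

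| SD (mm) | b = 0: p | k = 10 | k = 20 | b = 1 mm: p | k = 10 | k = 20 |
|---|---|---|---|---|---|---|
| 0.5 | 0.0001 | 0.06% | 0.13% | 0.0228 | 20.6% | 36.9% |
| 0.75 | 0.0077 | 7.4% | 14.3% | 0.0912 | 61.6% | 85.2% |
| 1.0 | 0.0455 | 37.2% | 60.6% | 0.1600 | 82.5% | 96.9% |
| 1.5 | 0.1824 | 86.7% | 98.2% | 0.2752 | 96.0% | 99.8% |
| 2.0 | 0.3173 | 97.8% | 99.95% | 0.3753 | 99.1% | 99.99% |

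Example, SD 1.0 mm and b = 0: p = 2 × (1 − Φ(2)) = 0.0455; 1 − 0.9545^10 = 0.372; 1 − 0.9545^20 = 0.606. Intermediate within-patient correlations of 0.9 and 0.5 give 48.5% and 57.9%. With b = 0 the chance passes 50% at an SD of 1.09 mm (k = 10) or 0.94 mm (k = 20).

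**A case that needs no SD.** If b = 2 mm and errors are symmetric, at least half of the distribution of the difference lies at or beyond 2 mm, so p ≥ 0.5 whatever the SD. With ten independent patients, the chance is at least 1 − 0.5^10 = 99.9%. Because b is only the difference between methods, the result is the same whether OPIE or TEE carries the offset.

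**Direction.** Down each column the chance rises with the SD, and at each SD it rises with the bias. If every difference is below 2 mm, the rule is not met.

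**The case against.** The best defence is that the investigators take OPIE's accuracy as already supported. Section 3 reports a simulation in which probe and conventional measurements corresponded 1:1. On that premise a 2 mm discordance is information TEE did not supply, and one such patient may matter. But the simulation is reported without figures, was not done in patients and is not part of the rule. The rule assumes OPIE is accurate and does not test it.

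The planned mean and SD would also reveal a 2 mm average bias. That is true, and the descriptive analysis is sound as far as it goes. But these summaries have no threshold and no stated role in the declaration of utility.

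The analysis paragraph labels the pairs as before and after bypass, which read literally puts both readings of a pair in the same period. This loosens the different-state point, which is an inference across sections. Sections 1 to 3 support it, and the main conclusion does not depend on it.

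The noise-only probabilities run from about 0.1% to above 99.9% on an unstated SD, and nothing in the documents shows that a 2 mm bias exists. The figures therefore illustrate the rule and do not predict this trial.

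Finally, this is a ten-patient pilot whose results Section 4 calls preliminary. That limits the harm, but it sits badly with a rule that lets one reading show utility.

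**Conclusion.** The concern holds, and the rule must be changed. It cannot separate a useful probe from an inaccurate one, and it favours the inaccurate one. That conclusion follows from the wording and needs no assumed SD.

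The size does depend on assumptions. With a 2 mm mean difference, symmetric errors and independent patients, the rule is met at least 99.9% of the time. With no true difference and normal errors, it is rarely met by chance at an SD of 0.5 mm, and more often than not once the SD exceeds roughly 0.9 to 1.1 mm. Even at an SD of 0.5 mm, a 1 mm probe bias gives 21–37%.

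**What to change.** Delete the statement that any single difference of 2 mm or more shows utility. Replace it with:

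- the mean OPIE–TEE difference and its SD (already planned), plus 95% limits of agreement (mean ± 1.96 SD), with 95% confidence intervals for the mean and for each limit, separately before and after resection;
- the number of patients with an absolute difference of 2 mm or more, with an exact 95% confidence interval, labelled as discordance between methods and not as utility;
- the number of the 20 planned OPIE readings obtained, by time point, which answers the visualisation question in Section 1.

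State that these data alone will not support a claim that OPIE is more accurate than TEE. At most, each method's before-minus-after change could be set against the specimen thickness, which Section 4 already collects, as a descriptive and exploratory analysis. A constant offset cancels in that change and would not be detected.

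The cost is one reworded paragraph, with no extra patients, measurements or procedures. Utility can no longer be claimed from one discrepant reading, and the utility objective in Section 2 is then answered descriptively, without a pass criterion. Precision at n = 10 is low:

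- mean difference: t(0.975, 9)/√10 = ±0.72 SD;
- each limit of agreement: t(0.975, 9) × √(1/10 + 1.96²/18) = ±1.27 SD;
- 1 of 10 patients discordant: exact 95% interval 0.3% to 44.5%;
- 10 of 10 readings obtained at a time point: lower limit 69.2%.

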#### **5. SUBJECTS POPULATION SELECTION**

Patients who are seen by in the Hypertrophic Cardiomyopathy (HCM) Clinic and will undergo surgical

myectomy for management of their HCM will be considered for this study.

### **5.1 Inclusion Criteria**

All patients, inclusive of male and female and all racial/ethnic origins, age 18 or older who are scheduled to receive a septal myectomy.

### **5.2 Exclusion Criteria**

Less than 18 years of age

### **5.3 Subject Withdrawal Criteria**

Subjects may withdraw consent from the research and revoke authorization for the use and disclosure of protected health information at any time. Subjects may not revoke authorization for uses or disclosures that have already made or must make to complete analyses or report data from research in progress. If the subject withdraws consent but does not revoke authorization, the subject's health information may continue to be disclosed for research as described in this protocol.

To withdraw consent and/or revoke authorization, subjects may contact the Principle Investigator in writing.

## **6. POTENTIAL BENEFITS TO SUBJECTS**

There will not be an immediate benefit to subjects enrolled in this study. This study seeks to improve the ability to monitor the depth of surgical septal myectomy during the on-pump period in the OR. This might lead to improved clinical care in the future.

## **7. POTENTIAL RISKS TO SUBJECTS**

There are minimal risks to subjects. Although health information that is collected will be kept in a secure server, there is always the risk that it may be accessed by individuals not associated with this study. Efforts will be made to protect confidentiality as outlined in this protocol. We estimate that the cardiopulmonary bypass time of the OPIE will be prolonged by 3 minutes. This may be offset by faster myectomy time gained by more confidence of septal thickening. This potential increased confidence in performing the myectomy by knowing the thickness of the septum highlights the equipoise that provides the rationale for this research. Given the usual cardiopulmonary bypass time for HCM surgery

of 60 minutes a 3 minute prolongation of this time is clinically not significant. Therefore we believe that the OPIE procedure poses no clinical risk for the patients. However, we will monitor for risk by the procedures specified below. The device is small and is used under direct visualization without the need for any pressure against tissue, so there is no risk of perforation. The device is a sterile single-use object and therefore would have no additional risk of infection. The interior of the left ventricle, where the device would be used is full of blood and therefore there could not be any bleeding risk.

#### **8. Subject Recruitment and Compensation**

Subjects will be drawn from patients seen at the Hypertrophic Cardiomyopathy (HCM) Clinic and those scheduled to undergo septal myectomy cardio surgery within the New York University Langone Medical Center. These subjects will be under the care of both the PI and the co-investigator. The study will be described by the PI and consent will be obtained > 1 day after this initial description. Consent will be obtained by the PI or co-investigators in a private setting either in the PI office or co-investigators or in the hospital room. Informed consent will be obtained prior to the surgery. The subject will be given adequate time to read the consent form, ask questions, and consider study participation. All questions and/or clarifications, which the subject may have or need, will be addressed to their satisfaction before the consent is signed. Most of the patient's data will be gathered from the medical chart; however, the subject may be asked some questions regarding changes or latest updates in his/her current medications. Informed consent for this study, scanned into EPIC, will be confirmed at the time-out prior to surgery.

This study provides no additional cost to a subject. There are no interventions or procedures involved in this study that would be billable to the subject other than the standard of care. Subjects will not receive compensation for their participation in this project.

#### **9. STUDY MANAGEMENT AND PERSONNEL**

The Principle Investigator for this research project will analyze and store the data. The Principle investigator will store the data on a secure NYU server on a locked computer, where access will be restricted to the PI and other members of the study.

All Investigators and study personnel involved in this study have completed the appropriate human subjects' research training (NYU CITI module).

## **10. CONFIDENTIALITY**

Data collected will also be de-identified and stored in the database using coded identification as well. The data will be linked to the subject's medical record number. Access to the key code linking the coded identification to the patient's medical record number will be restricted to the principle investigator, co-investigators and research staff. All data, including the key code, will be stored on a secure, password protected computer server housed in the Department of Cardiothoracic Surgery.

Data provided to requesting researchers will be stripped of identifiers. Only the principle investigator, co-investigators and research staff listed on this protocol will have access to the key code linking the specimen and data to the subject's medical record number. The de-identified information allowed to investigators will always be subject to prior IRB review and approval.

### **Data Safety Monitoring Plan**

[name], Director of Echocardiography will be responsible for monitoring the conduct and safety of the study. [name] is Associate Professor, Department of Medicine and Clinical Director, Non-Invasive Cardiology.

[name] will review the chart and clinical course of the patients to confirm safety of the performance of the protocol. He will review safety after every other case. All complications will be noted and he will evaluate whether there is relation to the OPIE: mortality, infection, cerebrovascular events. Complications will be determined to be either definitely related, possibly related, or definitely unrelated.

If there is a definite or possible relation of a complication to the OPIE, the adverse event will be reported to the IRB within a week of the operation.

If there is an adverse event that is deemed definitely related to the OPIE the study will be stopped pending comprehensive review.

Reports from [name] will be forwarded to the IRB after 6 cases and after 10 cases.

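### The only written stopping rule needs a definitely related event; possibly related deaths, infections or strokes, in any number, trigger no pause under it

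*Combined protocol and SAP*

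**What the plan says.** The Data Safety Monitoring Plan, which follows section 10 under its own heading, makes one physician responsible for safety. On what is assessed, it says: "All complications will be noted and he will evaluate whether there is relation to the OPIE: mortality, infection, cerebrovascular events". On grading, it says: "Complications will be determined to be either definitely related, possibly related, or definitely unrelated". It gives no criteria for the three grades.

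Two consequences are attached to the grades:

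- Definite or possible: "If there is a definite or possible relation of a complication to the OPIE, the adverse event will be reported to the IRB", with a limit of one week from the operation.
- Definite only: "If there is an adverse event that is deemed definitely related to the OPIE the study will be stopped pending comprehensive review".

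There is also periodic oversight. The plan says of the monitor: "He will review safety after every other case". The monitor's reports "will be forwarded to the IRB after 6 cases and after 10 cases". It does not say what the monitor or the IRB does with a possibly related event once it has been seen or reported.

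On design, section 4 says "We will enroll 10 subjects in this pilot study" and describes no control group. Section 7 says "Therefore we believe that the OPIE procedure poses no clinical risk for the patients", and then points to the monitoring procedures as the check on risk.

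**The concern.** The stop depends on the grade that is hardest to assign in this design. Every patient has the probe used during a bypass operation. Section 7 estimates that OPIE adds 3 minutes to a usual bypass time of 60 minutes, which is 3/60 = 5%. Death, infection and stroke can also follow from the operation. There are no controls and no expected complication rates, so a single reviewer has little basis for certainty in either direction. The scale has nothing between possible and definite, and any event that can be neither attributed nor excluded with certainty belongs in the middle grade. That grade leads to a report but to no stated action on enrolment.

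What is at stake is the safeguard itself. The probe is off-label for this use (section 1), and section 7 relies on the monitoring plan in case the belief that there is no risk proves wrong. Two or three possibly related serious events in the early cases would each be reported, and nothing in the written rule would hold the next case until they had been reviewed together.

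**Working it through.** **What the text provides.** The plan gives no event threshold, complication rate or operating characteristic for the rule, so there is no figure of its own to reproduce. Its consequences by grade are:

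| Grade | IRB report within a week | Study stop |
|---|---|---|
| Definitely related | yes | yes, on the first event |
| Possibly related | yes | none stated, at any count |
| Definitely unrelated | no | none stated |

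**Inputs for an illustration.** n = 10 patients (section 4). Two quantities are assumptions, because the documents do not give them: p, the per-patient risk of a complication graded possibly or definitely related; and q, the share of those graded definite. Patients are treated as independent, with at most one such complication each, and probabilities refer to a full series of 10. The only complication rate in the documents is reoperation at 1-2% (section 3), which is not one of the three harms named in the monitoring plan.

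**Formulas.**

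- Two or more complications: 1 − (1 − p)^10 − 10p(1 − p)^9
- Written rule fires: 1 − (1 − pq)^10

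**Worked case, p = 0.20 and q = 0.10.**

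- Two or more: 1 − 0.80^10 − 10(0.20)(0.80^9) = 1 − 0.1074 − 0.2684 = 0.624
- Rule fires: 1 − 0.98^10 = 1 − 0.8171 = 0.183
- Two or more, none graded definite: 0.98^10 − [0.80^10 + 10(0.18)(0.80^9)] = 0.8171 − [0.1074 + 0.2416] = 0.468

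The 62.4% and 18.3% are both shares of all 10-patient studies under these assumptions; the second is not conditional on the first. The third line is the direct measure of the gap: in about 47% of such studies there would be two or more possibly related complications and no stop under the written rule.

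**Range.**

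| p | two or more in 10 | rule fires, q = 0.10 | rule fires, q = 0.25 |
|---|---|---|---|
| 2% | 1.6% | 2.0% | 4.9% |
| 5% | 8.6% | 4.9% | 11.8% |
| 10% | 26.4% | 9.6% | 22.4% |
| 20% | 62.4% | 18.3% | 40.1% |
| 30% | 85.1% | 26.3% | 54.1% |

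With q = 0 the rule never fires, but that only restates the assumption. A pause spares patients only if it comes before the last cases. By the review after case 8, with p = 0.20 and q = 0.10, two or more complications have occurred with probability 49.7% and the rule has fired with probability 14.9% (the same formulas with 8 patients).

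**Cost of a wider trigger.** Now let p be a background rate, meaning events caused by the operation but graded possibly related.

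- Pause on the second event only: 8.6% at p = 0.05 and 26.4% at p = 0.10, from the table.
- Pause on any death or on the second event, with one fifth of events assumed fatal. No pause needs either no event or exactly one non-fatal event.
  - p = 0.05: 1 − [0.95^10 + 10(0.04)(0.95^9)] = 1 − [0.5987 + 0.2521] = 14.9%
  - p = 0.10: 1 − [0.90^10 + 10(0.08)(0.90^9)] = 1 − [0.3487 + 0.3099] = 34.1%

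**The case against.** The strongest reply is that possibly related events are not ignored. A designated monitor reviews every two cases, each such event reaches the IRB within a week, and reports follow after 6 and 10 cases. In a 10-patient pilot, case-by-case judgement is a legitimate alternative to a count. This stands in part. A reader might infer that repeated possibly related harms could never pause the study; the documents do not support that, because a discretionary pause is neither provided for nor excluded. What they do show is that no pause is required.

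A reader might also infer that the rule can hardly ever fire. That too goes beyond the text. Without grading criteria, q is unknown, and at p = 0.20 the rule fires in 18.3% of studies if q = 0.10 but in 40.1% if q = 0.25. The stop sentence covers any adverse event, and a local injury seen while the probe is in use under direct vision might be attributed to it without controls. The weakness is clearest for the three named harms.

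Two further points stand. A count of possibly related events does not separate device harm from operative harm: the same binomial probability is a benefit or a cost depending on the cause. And the large gaps need rates of 20-30%, which no document figure supports; at 2%, two or more events are rare (1.6%) and the written rule is slightly more likely to fire (2.0% at q = 0.10). A threshold of two is therefore open to debate. The case for acting on a single possibly related death does not depend on these rates.

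**Conclusion.** The concern holds in a limited form. The written plan specifies reporting for possibly related complications but no action on enrolment, whatever their number or severity, and in this uncontrolled surgical series that is the grade most ambiguous serious events will tend to receive. That tendency is an inference from the design and the scale, not a documented fact.

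The size of the gap depends on two unknowns. At the assumed 20% rate with 10% graded definite, repeated events would be common (62%) and the written rule would usually stay silent (firing in 18%). At low rates, or with a larger definite share, the gap narrows. This is a weakness in the stopping rule that is cheap to close. It is not a contradiction or a statistical error, and it does not show that monitoring is absent.

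**What to change.** In the Data Safety Monitoring Plan, extend the existing study-level stop for comprehensive review so that it also applies to any death graded possibly related. Add a pause of enrolment for the same review on repeated possibly related complications, with the count set by the sponsor and the IRB; the second event is one example. Keep the present rule for definitely related events.

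The drafting cost is a sentence or two. The operating cost is an occasional pause for events due to the operation: 8.6% or 26.4% of studies for a second-event trigger alone, at assumed background rates of 5% or 10%, and about 15% or 34% with the death trigger added and one fifth of events assumed fatal. In a 10-case pilot such a pause should be a short delay. The change concerns the conduct of the study only and alters no patient's care.
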